#### At study entry:

Patients on this trial who have lesions requiring radiation prior to initiation of systemic therapy in the view of the treating physician will be allowed to get such radiation. This will not limit their trial participation, though the lesion will be noted as having been radiated.

#### After 10 weeks of ceritinib monotherapy:

Lesions that persist after ceritinib monotherapy will receive stereotactic radiation. These include lesions that may have progressed during ceritinib monotherapy alone. As long as no change in systemic therapy is indicated, these patients will continue on the trial. Up to 6 sites or organs will receive stereotactic radiation, at the discretion of the treating physician. All sites of gross tumor (typically defined by CT and PET) should be treated for patients to continue on study.

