### **1.4 Study rationale and purpose**

Patients with *ALK*+ non small cell lung cancer will receive the current optimal therapy with ceritinib. After 10 weeks of targeted therapy, there will likely be some persisting lesions that would not have completely regressed. These persisting lesions would likely consist of cells that are less sensitive to targeted therapy. From the data summarized above [13], these persisting lesions are most to subsequently develop resistance and demonstrate progression.

To delay the onset of clinical progression, lesions that persist after 10 weeks of ceritinib therapy and are amenable to stereotactic ablative radiation will be radiated. Ceritinib will be held for 3 days before the first dose of radiation and resumed 3 days after the last dose. There is no specific window for radiation. SABR should be initiated as feasible following at least 10 weeks of ceritinib treatment.

After radiation, all patients will continue ceritinib therapy. If subsequently there is any evidence of progression, there will be an assessment of whether a repeat course of radiation is feasible. If it is feasible to repeat SABR to sites of progression, this will be performed and ceritinib resumed. If SABR is not possible, then a change in systemic therapy will be required.

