### 2.2.1 Treatment phase and duration of treatment

Patients eligible for treatment will receive 450 mg daily of ceritinib as part of a 28 day cycle. The first dose of each cycle will be administered after evaluation at the study center. Patients will remain on study and take ceritinib until there is evidence of disease progression by RECIST 1.1, unacceptable toxicity, withdrawal of consent, or discontinuation of the trial for any other reason. In case of oligoprogression amenable to repeat courses of SABR, the treating oncologist may resume ceritinib if it is indicated per standard clinical practice. Patients must continue to be followed for safety and efficacy assessments as per the schedule of assessments.

After 2 treatment cycles, lesions will be assessed by treating physician per RECIST 1.1. Persisting lesions will be treated with a course of SABR as feasible following at least 10 weeks of ceritinib treatment. Ceritinib will be held 3 days before the start of radiation. Patients will resume ceritinib 3 days

after completion of the SABR. Regular surveillance will follow and any new or enlarging lesions that develop will be assessed for repeat SABR.

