#### 4.1.2 Treatment duration

Patients will continue ceritinib treatment until they experience any of the following:

- Disease progression not amenable to SABR and necessitating change in systemic therapy determined by the treating physician.
- Unacceptable toxicity that precludes further treatment.
- Start of a new anti-cancer therapy.
- Pregnancy.
- Treatment is discontinued at the discretion of the investigator or patient.
- Lost to follow-up.
- Death.
- Completed.

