### **5.2.2 Treatment period**

Following completion of screening procedures and verifying patient eligibility, the patient will be approved for treatment per protocol.

The study treatment phase begins on Cycle 1, Day 1 with the first administration of ceritinib and will continue to receive ceritinib treatment until disease progression by RECIST1.1 not amenable to SABR necessitating a change in systemic therapy, unacceptable toxicity, withdrawal of consent, or discontinuation of the trial for any other reason whichever occurs first. Patients who have RECIST-defined PD as assessed by the investigator but who, in the opinion of the investigator, have evidence of continued clinical benefit from ceritinib may continue to receive the study medication upon approval by the principal investigator. In such cases, these patients must continue to be followed for safety and efficacy assessments as per the schedule of assessments. Patients will be assessed as per visit schedule in Table 5-1.

There is a visit windows of  $\pm 3$  days for scheduled study assessments.

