##### Prescription Dose

Number of Fractions	Total Cumulative Dose Encompassing 95% of Planning Target Volume		
	Protocol Compliant	Variation Acceptable	Deviation Unacceptable
1	21-27 Gy	<21 Gy but $\geq$ 16 Gy	<16 Gy or >27 Gy
3	26.5-33 Gy	<26.5 Gy but $\geq$ 24.5 Gy	<24.5 Gy or >33 Gy,
5	30-37.5 Gy	$\geq$ 28 Gy, <30 Gy	<28 Gy or >37.5 Gy,

Treatment may be delivered on consecutive days with 18 hours between fraction or every other day as deemed appropriate by the treating Radiation Oncologist.

If there is residual disease not amenable to SABR fractionation schemes proposed in the study, especially for bulky hilar or mediastinal disease, a fractionation schema of 45 Gy in 15 fractions may be employed, with adherence to standard normal tissue constraints outlined in the trial. This treatment will be delivered daily for three weeks.

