### 8.6.4 Normal Tissue Dose Constraints

In accordance with the prior Phase I studies [7, 8], certain normal tissue dose constraints must be respected.

The possibility that SABR-induced fibrosis might cause occlusion of large central airways, thus impeding ventilation distal to the occlusion has been well considered. An adjustment to the fractionation scheme may be made if, in the opinion of the treating radiation oncologist, the following conditions apply: (1) the location of a lung lesion is close enough to a large proximal bronchial airway such that occlusion might occur, and (2) compromised ventilation to the segment(s) of lung potentially affected would cause clinically significant adverse consequences.

The same special condition applies in the setting of a patient whose primary lung disease has not been irradiated previously but is present as a PET-positive site of disease, often in proximity to mediastinal structures which is a dose-limiting concern. These patients will be considered by the PI on a case-by-case basis.

The following table lists the specific organ and dose fractionation constraints on normal tissues.

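### Section 1.3.3 has two rules for staying on study after week 10 that can disagree; applying the stricter one under the composite PFS would turn a non-progressing patient into an event

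*Combined protocol and SAP*

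**What the plan says.** **Week 10.** Section 1.3.3 (After 10 weeks of ceritinib monotherapy) says that persisting lesions, including any that grew on ceritinib alone, are irradiated and that these patients continue provided no systemic change is indicated. It then sets a limit, "Up to 6 sites or organs will receive stereotactic radiation, at the discretion of the treating physician", and closes with "All sites of gross tumor (typically defined by CT and PET) should be treated for patients to continue on study".

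**Other sections on the same step.**
- Section 1.4: "lesions that persist after 10 weeks of ceritinib therapy and are amenable to stereotactic ablative radiation will be radiated".
- Section 2.2.1: "Persisting lesions will be treated with a course of SABR as feasible following at least 10 weeks of ceritinib treatment".
- Section 4.1.2, first reason to stop ceritinib: "Disease progression not amenable to SABR and necessitating change in systemic therapy determined by the treating physician".
- Section 5.2.2: treatment runs until "disease progression by RECIST1.1 not amenable to SABR necessitating a change in systemic therapy", or toxicity, withdrawal or another discontinuation.

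None of these lists stable, unirradiated tumor as a reason to leave.

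**The primary endpoint.** Section 2.0 and the endpoint table in 9.1 count RECIST progression, unacceptable toxicity, withdrawal of consent and any other discontinuation of the trial as PFS events. Section 1.3.3 (Subsequent areas of progression) runs PFS to the first progression. Section 2.0 for Cohort B, and the text above the 9.1 table, use time to subsequent systemic therapy. Section 9.10.1 mentions censoring in its heading but gives no rule.

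**Follow-up.** Table 5-1 schedules imaging at screening and during treatment cycles. Its long-term follow-up column holds only the survival assessment. Section 5.1.16 adds new therapy.

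**The concern.** Take a patient who is responding at week 10 but has residual disease that cannot all be irradiated. This patient meets the first continuation rule in section 1.3.3 and fails the last. Nothing in the protocol says which rule prevails.

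If the patient is taken off study, the composite PFS records an event with no progression. Feasibility of radiation, not tumor growth, would then set the primary outcome. The historical control is ceritinib alone, where no event can arise this way, so the comparison would be uneven. With 18 and 15 patients, one such event is visible in the result. And once the patient is off treatment, the protocol does not schedule the scans that would date the real progression.

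**Working it through.** **1. Who could be affected.** Several provisions shrink the group:
- Section 2.2 requires participants to be eligible for radiation as well as ceritinib.
- Section 8.3.2 has a fallback that begins "If there is residual disease not amenable to SABR fractionation schemes proposed in the study" and allows 45 Gy in 15 fractions.
- Section 8.3.3 makes gastrointestinal and cutaneous metastases ineligible. Sections 8.7 and 8.7.3 do the same for more than 10 brain lesions, brain lesions above 4 cm, and brain lesions that cannot meet the dose limits.
- Section 8.6.4 says "certain normal tissue dose constraints must be respected", but allows adjusted fractionation near large airways and case-by-case review of unirradiated primaries.
- The limit counts sites or organs, so several lesions in one organ need not exceed it.

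What remains is, for example, more than 6 extracranial sites or organs, or an extracranial lesion that fails the constraints by every permitted route. Section 3 sets no limit on the number of sites at entry, so the group need not be empty. The documents give no frequency.

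**2. How the same patient is scored.**

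| PFS definition | Removal without progression |
|---|---|
| Composite (2.0; 9.1 table) | event at removal |
| First progression (1.3.3) | not an event |
| Time to subsequent systemic therapy (2.0 Cohort B; 9.1 text) | not an event |

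**3. The planned sample sizes.** Inputs from 9.2: medians 10 vs 20 months (A) and 7 vs 14 (B), two-sided alpha 0.1, power 80%, accrual 36 months, follow-up 12 months. With hazard λ = ln 2/median, the event probability is p = 1 − [exp(−12λ) − exp(−48λ)]/(36λ). This gives p0 = 0.840, p1 = 0.623 (A) and p0 = 0.917, p1 = 0.742 (B). A one-sample exponential test on the log hazard needs n = [(1.645/√p0 + 0.842/√p1)/ln 2]²:
- A: 17.04, rounded up to 18 (plan: 18).
- B: 15.11, rounded up to 16 (plan: 15).

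The plan's figures are reproduced to within one patient.

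**4. Effect of one such event on the median.** Week 10 is L = 2.3 months. Expected event-free at L under the alternative: 18 × 0.5^(2.3/20) = 16.6 (A); 15 × 0.5^(2.3/14) = 13.4 (B). One patient is f = 1/16.6 = 6.0% or 1/13.4 = 7.5% of these. Scored as an event at L, the median is m × log2[2(1 − f)]:
- A: 20 × log2(1.880) = 18.2 months.
- B: 14 × log2(1.851) = 12.4 months.

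If the patient is instead followed and reverts to the control hazard, solving 0.5^(L/m) × [(1 − f) × 0.5^((t−L)/m) + f × 0.5^((t−L)/m0)] = 0.5 gives t = 19.2 (A) and 13.35 (B).

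**5. Effect on power.** Section 9.3 names only Kaplan-Meier for PFS, so the test is an assumption: one-sample log-rank, one-sided 0.05. Ranges cover the variances E and (E + O)/2. Simulation: 100,000 trials per cell, uniform accrual.

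| Patients affected and handling | Cohort A | Cohort B |
|---|---|---|
| none | 78-82% | 76-81% |
| 1, event at week 10 | 68-73% | 65-71% |
| 1, censored at week 10 | 76-81% | 74-78% |
| 1, followed, control hazard | 75-79% | 72-77% |
| 2, events at week 10 | 56-62% | 53-59% |
| 2, followed, control hazard | 70-76% | 67-73% |

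The one-sided false-positive rate with one such event falls from 3.6-5.1% to 1.9-2.9% (A) and from 3.5-5.0% to 1.9-2.8% (B).

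**6. Is the loss specific to this clause?** Moving the single event from 2.3 to 4 or 6 months leaves power at 68-73% (A) and 65-71% (B). The loss comes from adding one non-progression event, whatever its cause.

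**The case against.** The strongest reply is that the PFS definition, not section 1.3.3, does the damage. The composite turns every exit into an event. If PFS were settled on first progression or on time to subsequent systemic therapy, this exit would not count, even with section 1.3.3 unchanged. That stands. So does the point that the 10 points of power would be lost through any one withdrawal or toxicity exit.

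A reader might infer that the protocol requires such patients to be removed. It does not clearly do so. The sentence sits in a rationale section, says should, and follows a rule that lets patients continue. Nor do sections 2.2.1 and 5.2.2 contradict it: they are silent, and their catch-all for other reasons could absorb it.

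A reader might also infer that the progression date would be lost for good. The documents support less: no imaging is scheduled after end of treatment, but the scans are labelled standard of care and may well exist.

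Finally, insisting on complete irradiation fits the debulking rationale in 1.3.3 and is the sponsor's decision. The bias is also conservative, since the false-positive rate falls. All of this lowers the weight of the point. It does not remove the gap, because no section says how such a patient is scored.

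**Conclusion.** The point holds in a conditional form and is minor. Harm needs three things together: a patient whose residual disease cannot all be irradiated, a site that applies the last sentence of section 1.3.3, and use of the composite PFS. One such patient then costs about 10 points of power in either cohort, against 2-3 points if censored. The exit falls at week 10 or later, because section 1.4 fixes no window for SABR.

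The power figures assume exponential survival and a one-sample log-rank test. An exponential test, ln(E/O) × √O > 1.645, gives the same picture for one event: 78% to about 67-68% (A) and 76% to 65% (B). The gain from following the patient, about 6 points, further assumes reversion to the control hazard. The number affected is unknown and may be zero, so none of these figures predicts the trial's actual loss. The planned sample sizes are not in error on this account.

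**What to change.** Settle this together with the conflicting PFS definitions.

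1. Add to 2.0, 6.1.6 and the 9.1 table: *Inability to irradiate all residual sites is not a PFS event; these patients stay in the Full Analysis Set and are followed with the scheduled imaging to RECIST progression or death.*
2. Align the last sentence of section 1.3.3 (After 10 weeks) with 1.4 and 2.2.1: *All sites of gross tumor amenable to SABR, or to the 45 Gy in 15 fractions schedule, should be treated.*
3. Report the number of such patients per cohort.

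Whether they stay on protocol ceritinib is for the sponsor to decide. If complete irradiation is kept as a condition of treatment, item 1 still works: the patient leaves treatment but keeps the 8-weekly scans.

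Cost: a few sentences, and continued collection of standard-of-care scans in the few patients affected, if any. The downside is slight dilution of the SABR effect: with one such patient on the control hazard, power is about 75-79% (A) and 72-77% (B), against 78-82% and 76-81% with none.

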#### Subsequent areas of progression:

As long as the study participant is on ceritinib as the sole systemic therapy, further stereotactic radiation may be delivered to up to 6 sites or organs at a time. When ceritinib is no longer the systemic agent or when new progressive sites cannot feasibly be treated with stereotactic radiation (e.g., malignant pleural effusion or site previously irradiated), study participation will end. The primary endpoint of progression-free survival will be calculated from the start of treatment to the first episode of progression.

#### Ceritinib during stereotactic radiation:

Currently there are limited data about the safety of concurrent ceritinib and stereotactic radiation, though studies are ongoing. If there is a concern for the safety of the patient, ceritinib will be held for 3

days prior to and 3 days after the stereotactic radiation. The total expected duration of the stereotactic radiation is expected to range between 1-5 treatments, generally not exceeding 21 days from first to last radiation therapy.

#### CNS metastases:

Stereotactic radiation to CNS lesions that require therapy will be allowed. At study entry the presence of CNS lesions or their treatment with radiation will not constitute a restriction to study participation. Subsequently, progression in the CNS will not terminate study participation, and patients may receive stereotactic radiation to those areas.

Evaluation of CNS metastases will consist of an MRI or contrast enhanced CT performed at baseline and then as clinically indicated, but at least every 3 months. Patients without CNS involvement will not be required to have mandatory CNS imaging. All patients with new symptoms suspicious of CNS involvement will have urgent CNS imaging performed.

### **1.4 Study rationale and purpose**

Patients with *ALK*+ non small cell lung cancer will receive the current optimal therapy with ceritinib. After 10 weeks of targeted therapy, there will likely be some persisting lesions that would not have completely regressed. These persisting lesions would likely consist of cells that are less sensitive to targeted therapy. From the data summarized above [13], these persisting lesions are most to subsequently develop resistance and demonstrate progression.

To delay the onset of clinical progression, lesions that persist after 10 weeks of ceritinib therapy and are amenable to stereotactic ablative radiation will be radiated. Ceritinib will be held for 3 days before the first dose of radiation and resumed 3 days after the last dose. There is no specific window for radiation. SABR should be initiated as feasible following at least 10 weeks of ceritinib treatment.

After radiation, all patients will continue ceritinib therapy. If subsequently there is any evidence of progression, there will be an assessment of whether a repeat course of radiation is feasible. If it is feasible to repeat SABR to sites of progression, this will be performed and ceritinib resumed. If SABR is not possible, then a change in systemic therapy will be required.

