## 2.0 Study Objectives

The hypothesis is that delivering SABR to patients with persisting tumors 10 weeks after ceritinib will result in superior overall tumor control, prolong PFS for patients and lengthen the duration of ceritinib activity in patients with *ALK*+ lung adenocarcinoma.

Published experience suggests that median PFS for patients who have previously been treated with crizotinib is less with ceritinib than those who have never been treated with crizotinib (7 months vs 10 months) (Shaw et al, NEJM 2014). As a result patients enrolled on this study will be divided into cohorts on the basis of prior exposure to crizotinib.

The primary endpoint of this study will be Progression-Free Survival (PFS); defined as time from initiation of ceritinib to evidence of disease progression by RECIST 1.1, unacceptable toxicity, withdrawal of consent, or discontinuation of the trial for any other reason.

There may be progression in a specific localized region that is amenable to stereotactic radiation. If all existing lesions that enlarge and any new lesions that develop can still be effectively treated with stereotactic radiation, patients will be evaluated for repeat SABR therapy and ceritinib resumed. This will be at the recommendation of the treating physician according to standard practice. This will be defined as Time to 2nd SABR therapy and will be one of the secondary endpoints.

Similarly, if 3rd round of SABR can be safely provided with subsequent resumption of ceritinib, it will be defined as the Time to 3rd SABR therapy.

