**Hypothesis:**

The primary objective is to describe the PFS in patients undergoing study therapy. This is defined as evidence of disease progression by RECIST, unacceptable toxicity, withdrawal of consent, or discontinuation of the trial for any other reason.

Additional SABR to enlarging lesions will be permitted while on ceritinib, but no change in systemic therapy will be allowed. Patients who demonstrate oligo progression and have disease amenable to repeat courses of radiation therapy may resume ceritinib at the discretion of the treating oncologist until a change in systemic therapy is indicated.

The secondary objective of the study is to report overall survival and in *ALK*-positive lung adenocarcinoma. We will use Kaplan-Meier methods to estimate the overall survival. The rate of overall response and its 95% confidence interval will be estimated using exact binomial method. Response duration will be summarized for patients who responded. Descriptive summary statistics like median, 25% and 75% percentiles will be used.

The secondary objective is also to describe the time to subsequent SABR in patients undergoing study therapy. Patients will be retreated with SABR if feasible. After the initial SABR to persisting lesions, if new lesions appear or if existing lesions enlarge but are amenable to SABR, patients will remain on study and listed as not having progressed. This time to 2nd and 3rd SABR will be recorded and reported. The secondary endpoint will be recorded as time to 2nd and (if applicable) 3rd SABR therapy.

The safety objective of this study to report the toxicity profile of the combination of ceritinib and SABR therapy. Both are well tolerated and routinely used in non-small cell lung cancer.

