### **6.1.4 Response Criteria**

#### **6.1.4.1 Evaluation of Target Lesions**

Complete Response (CR): Disappearance of all target lesions, determined by two separate observations conducted not less than 4 weeks apart. There can be no appearance of new lesions.

Partial Response (PR): At least a 30% decrease in the sum of the longest diameter (LD) of target lesions, taking as reference the baseline sum LD. There can be no appearance of new lesions.

Progressive Disease (PD): At least a 20% increase in the sum of the LD of target lesions, taking as reference the smallest sum LD recorded since the treatment started, or the appearance of one or more new lesions.

Stable Disease (SD): Neither sufficient shrinkage to qualify for PR nor sufficient increase to qualify for PD, taking as reference the smallest sum LD since the treatment started.

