### 6.1.6 Progression-Free Survival

Progression Free Survival will be the primary endpoint for this study. If oligoprogression occurs that is amenable to repeat treatment with SABR, the ceritinib will be held and SABR therapy delivered. If the treating oncologist then feels the patient would benefit from continuing the ceritinib that will be permitted. The patient will however be deemed as having progressed even if ceritinib is resumed.

After the initial SABR to persisting lesions if new lesions appear or if existing lesions enlarge but are NOT amenable to SABR (necessitating a change in systemic therapy), the patient will have completed the therapeutic portion of the study.

Time to 2nd SABR is defined as the duration of time from the start of treatment to the time of development of new or enlarging lesions that are amenable to SABR and the progression does not require a discontinuation of ceritinib.

Time to 3rd SABR is defined in patients who have already received two rounds of SABR while on this study as the duration of time from the start of treatment to the time of development of new or enlarging lesions that are amenable to SABR and the progression does not require a discontinuation of ceritinib.

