## 8.2 Therapy Stereotactic Ablation Body Radiation (SABR)

### 8.3 SABR DOSE AND TECHNIQUES

SABR will begin 10 weeks after initiation of ceritinib for consolidation of residual disease sites.

Additional SABR treatments will be delivered to new distinct areas of disease that develop after that period at the discretion of the treating medical oncology/radiation oncology teams. PFS will at that point already been established, but patients will be followed for OS.

Stereotactic treatment is the targeting, planning, and directing of treatment fields guided to a target based on known 3-D coordinates related to reliable fiducial markers. This differs from conventional radiation therapy in which treatment is guided by skin or bony landmarks assumed to correlate to the target volume based on the initial simulation. SABR in this study will be delivered with an ablative range of dose per fraction. Treatment will account for inter/intra-fractional errors with careful dosimetry that delivers an ablative dose to the metastatic lesion(s) while respecting normal tissue constraints.

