**Study Design:**

**Purpose:** of this prospective, single-center, two cohort, non-randomized trial is to evaluate the impact of the combination of ceritinib and stereotactic radiation delivered to patients with *ALK*-rearranged adenocarcinoma. The enhanced efficacy of this combination is to be evaluated specifically with regards to prolongation of clinical benefit of ceritinib. We will also evaluate the safety of this combination of targeted therapy and radiation.

For *ALK*-rearranged patients started on ceritinib and treated with SABR to persisting lesions:  
 -PFS compared to published historical results with ceritinib alone PFS=7 month for prior crizotinib treated and 10 month for no previous crizotinib therapy (Shaw et al, NEJM 2014).  
 PFS will be defined as Time to Subsequent Systemic Therapy.

As secondary objectives, we will also report overall survival and time to 2nd and 3rd SABR for each cohort.

	Objective	Endpoint
Primary:	Cohort A: Superiority of ceritinib + SABR median PFS compared to historical control of 10 months (expected to be 20 months)  Cohort B: Superiority of ceritinib + SABR median PFS compared to historical control of 7 months	Cohort A Median PFS defined as time from initiation of ceritinib until disease progression by RECIST 1.1, unacceptable toxicity, withdrawal of consent, or discontinuation of the trial for any other reason including death.  Cohort B: Median PFS defined as time from initiation of ceritinib until disease progression by RECIST 1.1, unacceptable toxicity, withdrawal of consent, or discontinuation of the trial for any other reason including death.
Secondary:	Report Overall survival  Report Time to 2 nd SABR  Report Time to 3 rd SABR  Report proportion of patients CR/PR/stable disease at 6 and 12 months	Overall survival  Time from start of systemic therapy to first day of second course of SABR  Time from start of therapy to first day of third course of SABR  Number of patients with CR/PR/stable disease for 6 and 12 months after initiation
Safety:	Demonstrate safety of ceritinib followed by SABR	Describe toxicity and adverse events (CTCAE v.4) compared to historical controls.

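### The plan does not settle whether progression treated with repeat SABR ends PFS: some sections count it as the event, others do not, and growth below the RECIST threshold has no stated status

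*Combined protocol and SAP*

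**What the plan says.** **When repeat SABR comes into play.** Section 1.4: "If subsequently there is any evidence of progression, there will be an assessment of whether a repeat course of radiation is feasible". Section 2.2.1: "any new or enlarging lesions that develop will be assessed for repeat SABR". The closing text of Section 2.0 (under Hypothesis): "Additional SABR to enlarging lesions will be permitted while on ceritinib". None of these gives a size threshold.

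**What ends PFS.** Section 2.0 opens with PFS "defined as time from initiation of ceritinib to evidence of disease progression by RECIST 1.1", and the Section 9.1 endpoint table repeats it for both cohorts: "Median PFS defined as time from initiation of ceritinib until disease progression by RECIST 1.1". Unacceptable toxicity, withdrawal and any other discontinuation also count. For target lesions, Section 6.1.4.1 sets progression at "At least a 20% increase in the sum of the LD of target lesions", measured from the smallest sum; any new lesion is also progression.

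**Sections that count SABR-treated progression as the event.** Section 6.1.6, on oligoprogression given repeat SABR: "The patient will however be deemed as having progressed even if ceritinib is resumed". Section 8.3, on additional SABR to new areas of disease: "PFS will at that point already been established, but patients will be followed for OS". Section 1.3.3 (subsequent areas of progression) stops PFS at the first progression episode.

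**Sections that do not.** The closing text of Section 2.0 keeps patients whose new or enlarging lesions can be treated with SABR on study and counts them as progression-free. Section 5.3.1 reserves the progressed label for disease that SABR cannot treat and that needs a systemic change. The Cohort B primary endpoint in Section 2.0, and the Section 9.1 text above its table, equate PFS with time to subsequent systemic therapy.

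Section 9.10.1, whose title includes censoring, says only that missing data are not imputed.

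**The concern.** The primary comparison sets median PFS in each cohort against a published ceritinib-alone figure: 10 months for Cohort A and 7 for Cohort B. Nothing in the documents describes local salvage before progression in that benchmark. If a patient's progression can be irradiated and then not counted, the trial's PFS runs past the point where it would otherwise have stopped.

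The trial is open-label and single-center. The treating physician assesses the lesions and also recommends repeat SABR. A favourable median could then partly reflect how later growth was handled and recorded, rather than the consolidation at about week 10 that the trial is meant to test. Two analysts working from different sections could also report different PFS times for the same patient.

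**Working it through.** **1. The sections side by side**

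| Section | RECIST progression, treatable with SABR | Existing lesion re-irradiated, target sum below +20% |
|---|---|---|
| 2.0 opening definition; 9.1 table | Event | No event |
| 1.3.3 | Event | Unclear; an episode of progression is not defined |
| 6.1.6 | Event if called oligoprogression | Depends on a word with no RECIST or size definition |
| 8.3 | Event already reached (new areas) | Not addressed |
| 2.0 closing text | No event | No event |
| 5.3.1 | No event | No event |
| 2.0 Cohort B endpoint; 9.1 text above table | No event until systemic therapy changes | No event until systemic therapy changes |

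The middle column is the larger fault, because full RECIST progression is an event in some rows and not in others. The right-hand column is the smaller gap.

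**2. Can the smaller gap occur?** Section 6.1.2 allows up to six target lesions. Take six of 15 mm, a sum of 90 mm. If one doubles to 30 mm, the sum is 105 mm and 105/90 − 1 = +16.7%, which is stable disease. With five such lesions the sum goes from 75 to 90 mm, exactly +20%, which is progression. The gap exists but depends on the configuration.

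**3. The plan's own sample sizes.** Inputs from Section 9.2: medians 10 v 20 (A) and 7 v 14 (B), two-sided 0.10, 80% power, accrual 36 months, follow-up 12 months. With λ = ln 2/m and uniform accrual, the event probability is P(m) = 1 − [e^(−12λ) − e^(−48λ)]/(36λ), and N = [1.645/√P0 + 0.842/√P1]² / (ln 2)².

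- Cohort A: P0 = 0.840, P1 = 0.623; (1.795 + 1.066)²/0.4805 = 17.04, so 18 as stated.
- Cohort B: P0 = 0.917, P1 = 0.742; (1.718 + 0.977)²/0.4805 = 15.11, against 15 stated; power at 15 is 79.8%.

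Both reproduce, so the sample sizes are not at issue.

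**4. Size if events go uncounted.** The share f of patients affected is not in the documents and is assumed. The true median is set at the benchmark. Section 9.3 names no test for the comparison with the benchmark, so one-sample exponential tests at upper-tail 0.05 are also assumed (200,000 simulated trials per setting).

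*Model (a): the first event is replaced by one full further exponential interval.* Survival is e^(−x)(1 + f·x) with x = λt. Setting this to 0.5 gives x = 0.767, 0.850 and 0.942 for f = 10%, 20% and 30%. The apparent median is (x/0.693) times the benchmark.

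| f | A: median, false-positive rate | B: median, false-positive rate |
|---|---|---|
| 0 | 10.0, 0.036 | 7.0, 0.031-0.034 |
| 10% | 11.1, 0.081 | 7.7, 0.070-0.076 |
| 20% | 12.3, 0.151 | 8.6, 0.129-0.140 |
| 30% | 13.6, 0.249 | 9.5, 0.208-0.224 |

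The ranges for B are the cube-root exponential test and the one-sample log-rank test.

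*Model (b): the event is only postponed*, by 1.84 months (one 8-week scan interval), 3.68 or 6 months, in 10-50% of patients, for events after 2.3 months. Cohort A: median 10.2-13.3, false-positive rate 4-14%. Cohort B: median 7.2-10.4, 4-17%.

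*Model (c), an upper bound: events removed for good*, so the median is the benchmark/(1 − f). For f = 10-30%, Cohort A: 11.1-14.3 months, 8-34%. Cohort B: 7.8-10.0 months, 8-33%.

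**The case against.** The best defence is that the intent can be read from the plan. Section 6.1.6 says outright that repeat SABR for oligoprogression counts as progression, and it describes the new or enlarging lesions behind a second course as progression. Section 6.1.5 ties time to subsequent SABR to objectively documented recurrence or progression, judged against the smallest measurements. Sections 1.3.3 and 8.3 agree. Sections 1.4 and 2.2.1 call for an assessment, not automatic irradiation.

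The sub-threshold case is also confined. New lesions are always progression. Section 1.3.3 wants all gross disease treated after the first 10 weeks, and names a previously irradiated site as an example where further SABR is not feasible. Participation then ends, and discontinuation is itself a PFS event. The six lesions in the example would normally have been irradiated already if they persisted.

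Finally, repeat SABR belongs to the strategy under study. If the benchmark counted only RECIST events (the documents do not say), counting smaller growth here would bias PFS downward.

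Most of this stands. A reader might infer that re-irradiating any enlarging lesion always removes the primary event. The documents do not support that, because three sections point the other way. A reader might also take the 64% known-site failure rate in Section 1.1.4 as the share affected. It describes a background study and says nothing about re-irradiation below the RECIST threshold.

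The defence does not remove the contrary lines in Sections 2.0, 5.3.1 and 9.1, and it supplies no definition of oligoprogression. Section 8.3 speaks only of new areas, so it does not reach an enlarging existing lesion.

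**Conclusion.** The point holds as an inconsistency in the primary endpoint, with a narrow undefined case inside it. Under the closing text of Section 2.0, Section 5.3.1 or the subsequent-therapy definition, even full RECIST progression treatable with SABR is not a PFS event. Under a RECIST-only reading, only sub-threshold re-irradiation escapes. Either way the bias lengthens PFS relative to the benchmarks. If the first repeat SABR is counted, no event is lost.

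The magnitude is a sensitivity range, not an estimate. It rests on an assumed share of patients, exponential PFS and an assumed test. Model (a) is demanding, since each affected patient gains a complete further interval; model (b) is milder and leaves the false-positive rate near its starting value when few patients are affected or delays are short. The documents therefore do not support a claim that the result will be inflated by a given amount. They do show that the event rule for repeat SABR must be fixed before the primary analysis.

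**What to change.** Use one PFS definition in Section 2.0 (opening text, both cohort endpoints and closing text), Section 5.3.1, Section 6.1.6 and Section 9.1. Suggested wording: PFS ends at the earliest of RECIST 1.1 progression, the other listed events, or, if a repeat SABR course is given for a new or enlarging lesion before RECIST progression has been documented, the date of the imaging that prompted that course.

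In the same edit, delete or reconcile the Section 2.0 line that counts SABR-treatable growth as progression-free, the matching sentence in Section 5.3.1, and the lines equating PFS with time to subsequent systemic therapy. Keep that time as a separate endpoint.

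Record the prompting-imaging date for every repeat course. Section 6.1.6 dates the second SABR by the development of lesions and the Section 9.1 table by the first treatment day, so the needed date may not otherwise be captured. Add a sensitivity analysis that uses RECIST progression alone as the disease event.

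The cost is an edit to four sections, one data field and one extra analysis. Reported PFS may be slightly shorter, and the rule is somewhat conservative if the benchmark used RECIST-only events. Who receives repeat SABR, and when, is unchanged.
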